5.2.2 Coercion or Undue Influence during Consent

Describe the steps that will be taken to minimize the possibility of coercion or undue influence in the consent process.

Participants will be approached by a member of the research team and presented with the study opportunity. Participants will be given ample time to read and review the consent form on their own. All questions the participant may have will be answered, and written consent will be obtained. Consent will be obtained in accordance of principles of GCP and ICH guidelines.

5.3 Waiver of Written Documentation of Consent

Review "HRP – 411 – Checklist – Waiver of Written Documentation of Consent."

5.3.1 Indicate which of the following conditions applies to this research:

The research presents no more than minimal risk of harm to subjects and involves no procedures for which written consent is normally required outside of the research context.

OR

The only record linking the subject and the research would be the consent document and the principal risk would be potential harm resulting from a breach of confidentiality. Each subject will be asked whether the subject wants documentation linking the subject with the research, and the subject's wishes will govern. (Note: This condition is not applicable for FDA-regulated research. If this category is chosen, include copies of a consent form and /or parental permission form for participants who want written documentation linking them to the research.)

OR

If the subjects or legally authorized representatives are members of a distinct cultural group or community in which signing forms is not the norm, that the research presents no more than minimal risk of harm to subjects and provided there is an appropriate alternative mechanism for documenting that informed consent was obtained. (Note: This condition is not applicable for FDA-regulated research.)

Describe the alternative mechanism for documenting that informed consent was obtained:

[Type protocol text here]

5.3.2 Indicate what materials, if any, will be used to inform potential subjects about the research (e.g., a letter accompanying a questionnaire, verbal script, implied consent form, or summary explanation of the research)

Flyer and verbal script.

5.4 Informed consent will be sought but some of the elements of informed consent will be omitted or altered (e.g., deception).

Review "HRP-410-Checklist -Waiver or Alteration of Consent Process" to ensure that you have provided sufficient information.

5.4.1 Indicate the elements of informed consent to be omitted or altered

N/A

5.4.2 Indicate why the research could not practicably be carried out without the omission or alteration of consent elements

N/A

5.4.3 Describe why the research involves no more than minimal risk to subjects.

N/A

5.4.4 Describe why the alteration/omission will not adversely affect the rights and welfare of subjects.

N/A

5.4.5 If the research involves using identifiable private information or identifiable biospecimens, describe why the research could not be practicably be carried out without using such information or biospecimens in an identifiable format.

N/A

5.4.6 Debriefing

Explain whether and how subjects will be debriefed after participation in the study. If subjects will not be debriefed, provide a justification for not doing so. Add any debriefing materials to the study in CATS IRB.

N/A

5.5 Informed consent will not be obtained – request to completely waive the informed consent requirement

Review “HRP-410-Checklist -Waiver or Alteration of Consent Process” to ensure that you have provided sufficient information.

5.5.1 Indicate why the research could not practicably be carried out without the waiver of consent

N/A

5.5.2 Describe why the research involves no more than minimal risk to subjects.

N/A

5.5.3 Describe why the alteration/omission will not adversely affect the rights and welfare of subjects.

N/A

5.5.4 If the research involves using identifiable private information or identifiable biospecimens, describe why the research could not be practicably be carried out without using such information or biospecimens in an identifiable format.

N/A

5.5.5 Additional pertinent information after participation

Explain if subjects will be provided with additional pertinent information after participation. If not applicable, indicate “not applicable.”

N/A

5.6 Consent – Other Considerations

5.6.1 Non-English-Speaking Subjects

Indicate what language(s) other than English are understood by prospective subjects or representatives.

If subjects who do not speak English will be enrolled, describe the process to ensure that the oral and written information provided to those subjects will be in that language. Indicate the language that will be used by those obtaining consent.

Indicate whether the consent process will be documented in writing with the long form of the consent documentation or with the short form of the consent documentation. Review “HRP-091 –SOP- Written Documentation of Consent” and “HRP-103 -Investigator Manual” to ensure that you have provided sufficient information.

Subjects who do not understand spoken English will not be enrolled in the study. Members of the study team involved in the recruitment may not be fluent in other languages to interact with patients who do not understand spoken English.

5.6.2 Cognitively Impaired Adults

Refer “HRP-417 -CHECKLIST- Cognitively Impaired Adults” for information about research involving cognitively impaired adults as subjects.

5.6.2.1 Capability of Providing Consent

Describe the process to determine whether an individual is capable of consent.

Not applicable

5.6.2.2 Adults Unable to Consent

Describe whether and how informed consent will be obtained from the legally authorized representative. Describe who will be allowed to provide informed consent. Describe the process used to determine these individual's authority to consent to research.

For research conducted in the state of Pennsylvania, review “HRP-013 -SOP- Legally Authorized Representatives, Children and Guardians” to be aware of which individuals in the state of Pennsylvania meet the definition of “legally authorized representative.”

For research conducted outside of the state of Pennsylvania, provide information that describes which individuals are authorized under applicable law to consent on behalf of a prospective subject to their participation in the procedure(s) involved in this research. One method of obtaining this information is to have a legal counsel or authority review your protocol along with the definition of “children” in “HRP-013 -SOP- Legally Authorized Representatives, Children, and Guardians.”

Not applicable

5.6.2.3 Assent of Adults Unable to Consent

Describe the process for assent of the subjects. Indicate whether assent will be required of all, some or none of the subjects. If some, indicate which subjects will be required to assent and which will not.

If assent will not be obtained from some or all subjects, provide an explanation of why not.

Describe whether assent of the subjects will be documented and the process to document assent. The IRB allows the person obtaining assent to document assent on the consent document and does not routinely require assent documents and does not routinely require subjects to sign assent documents.

Not applicable

5.6.3 Subjects who are not yet adults (infants, children, teenagers)

5.6.3.1 Parental Permission

Describe whether and how parental permission will be obtained. If permission will be obtained from individuals other than parents, describe who will be allowed to provide permission. Describe the process used to determine these individual's authority to consent to each child's general medical care.

For research conducted in the state of Pennsylvania, review "HRP-013-SOP- Legally Authorized Representatives, Children and Guardians" to be aware of which individuals in the state of Pennsylvania meet the definition of "children."

For research conducted outside of the state of Pennsylvania, provide information that describes which persons have not attained the legal age for consent to treatments or procedures involved in the research, under the applicable law of the jurisdiction in which research will be conducted. One method of obtaining this information is to have a legal counsel or authority review your protocol along with the definition of "children" in "HRP-013-SOP- Legally Authorized Representatives, Children, and Guardians."

Not applicable

5.6.3.2 Assent of subjects who are not yet adults

Indicate whether assent will be obtained from all, some, or none of the children. If assent will be obtained from some children, indicate which children will be required to assent. When assent of children is obtained describe whether and how it will be documented.

Not applicable

6.0 HIPAA Research Authorization and/or Waiver or Alteration of Authorization

This section is about the access, use or disclosure of Protected Health Information (PHI). PHI is individually identifiable health information (i.e., health information containing one or more 18 identifiers) that is transmitted or maintained in any form or medium by a Covered Entity or its Business Associate. A Covered Entity is a health plan, a health care clearinghouse or health care provider who transmits health information in electronic form. See "HRP-103 -Investigator Manual" for a list of the 18 identifiers.

If requesting a waiver/alteration of HIPAA authorization, complete sections 6.2 and 6.3 in addition to section 6.1. The Privacy Rule permits waivers (or alterations) of authorization if the research meets certain conditions. Include only information that will be accessed with the waiver/alteration.

[Do not type here]

6.1 Authorization and/or Waiver or Alteration of Authorization for the Uses and Disclosures of PHI

Check all that apply:

Not applicable, no identifiable protected health information (PHI) is accessed, used or disclosed in this study. [Mark all parts of sections 6.2 and 6.3 as not applicable]

Authorization will be obtained and documented as part of the consent process. [If this is the only box checked, mark sections 6.2 and 6.3 as not applicable]

- Partial waiver is requested for recruitment purposes only (Check this box if patients' medical records will be accessed to determine eligibility before consent/authorization has been obtained). [Complete all parts of sections 6.2 and 6.3]**
- Full waiver is requested for entire research study (e.g., medical record review studies). [Complete all parts of sections 6.2 and 6.3]**
- Alteration is requested to waive requirement for written documentation of authorization (verbal authorization will be obtained). [Complete all parts of sections 6.2 and 6.3]**

6.2 Waiver or Alteration of Authorization for the Uses and Disclosures of PHI

6.2.1 Access, use or disclosure of PHI representing no more than a minimal risk to the privacy of the individual

6.2.1.1 Plan to protect PHI from improper use or disclosure

Include the following statement as written – DO NOT ALTER OR DELETE unless this section is not applicable because the research does not involve a waiver of authorization. **If the section is not applicable, remove the statement and indicate as not applicable.**

Information is included in the “Confidentiality, Privacy and Data Management” section of this protocol.

6.2.1.2 Plan to destroy identifiers or a justification for retaining identifiers

Describe the plan to destroy the identifiers at the earliest opportunity consistent with the conduct of the research. Include when and how identifiers will be destroyed. If identifiers will be retained, provide the legal, health or research justification for retaining the identifiers.

The linking list will be destroyed upon completion of the study. Additionally, any PHI will be destroyed or deleted upon completion of the study.

6.2.2 Explanation for why the research could not practically be conducted without access to and use of PHI

Provide an explanation for why the research could not practically be conducted without access to and use of PHI.

Information about type of repair and medication is needed for screening purposes.

6.2.3 Explanation for why the research could not practically be conducted without the waiver or alteration of authorization

Provide an explanation for why the research could not practically be conducted without the waiver or alteration of authorization.

The study team would be unable to identify the appropriate participants to be included in this research study.

6.3 Waiver or alteration of authorization statements of agreement

By submitting this study for review with a waiver of authorization, you agree to the following statement – DO NOT ALTER OR DELETE unless this section is not applicable because the research does not involve a waiver or alteration of authorization. **If the section is not applicable, remove the statement and indicate as not applicable.**

Protected health information obtained as part of this research will not be reused or disclosed to any other person or entity, except as required by law, for authorized oversight of the research study, or for other permitted uses and disclosures according to federal regulations. The research team will collect only information essential to the study and in accord with the “Minimum Necessary” standard (information reasonably necessary to accomplish the objective of the research) per federal regulations. Access to the information will be limited, to the greatest extent possible, within the research team. All disclosures or releases of identifiable information granted under this waiver will be accounted for and documented.

7.0 Study Design and Procedures

Data collection materials that will be seen or used by subjects in your study must be uploaded to CATS IRB (**Error! Hyperlink reference not valid.**). **DO NOT** include any actual data collection materials in this protocol (e.g., actual survey or interview questions)

[Do not type here]

7.1 Study Design

Describe and explain the study design.

This is a randomized clinical trial with two groups: control and stimulation. Participants will be randomly assigned to a NMES (active) treatment or control group in a 1:1 ratio. No stratification factors will be considered in the randomization process based on covariates such as gender, activity, and age. In the stimulation group, subjects will receive standard rehabilitation and NMES will be applied to calf muscles 6 weeks after repair surgery. The pad placement and stimulation parameters will be updated in a weekly basis for the stimulation group. The control group will follow standard rehabilitation and will not receive NMES. For both groups, ultrasound evaluation will be performed at week 6 and 12 weeks after surgery. The primary outcome (heel-rise) will be measured at week 12 after repair. Other outcomes (activity level, pain) will be measured daily for the first 6 weeks after repair.

7.2 Study Procedures

Provide a step by step description of all research procedures being conducted (broken down by visit, if applicable) including such information as below (where and when applicable); describe the following:

- HOW: (e.g., data collection via interviews, focus groups, forms such as surveys and questionnaires, medical/school records, audio/video/digital recordings, photographs, EKG procedures, MRI, mobile devices such as electronic tablets/cell phones, observations, collection of specimens, experimental drug/device testing, manipulation of behavior/use of deception, computer games, etc.)
- WHERE: (e.g., classrooms, labs, internet/online, places of business, medical settings, public spaces, etc.)

All participants participating will receive a standard rehabilitation protocol. All participants will be randomly assigned to NMES or control (standard of care) for the first 6 weeks after surgery. For the randomization process, a master list with patient codes will prepopulated with randomly assigned treatments (NMES vs control). As recruitment is performed, patients will be assigned a code with the corresponding intervention. The randomization will be performed at a 1:1 ratio between control and stimulation group. The research teams conducting the rehabilitation protocol at the Hershey Medical Center will instruct and evaluate all participants on how they place the electrodes, operate the NMES device (intensity combo II. This is a commercially available, FDA-approved device), and select the parameters to be used (Table 2 and Figure 2). The intensity will be set to the maximum comfortable intensity by the patient. Additionally, the research team will ensure the participants perform the procedure correctly at each weekly visit. The NMES device has an adherence meter to evaluate adherence to the protocol. Self-applied NMES intervention has been successfully used in several studies targeting muscle weakness after major knee surgeries [53], [54].

Table 2. Proposed NMES protocol

Week	Pad Placement	Time (min) x times per day
1	I, II, III	10 x 1
2-3	I, II, III	10 x 2
4-6	IV	20 x 2

Ultrasound evaluation: Cross-sectional area of the Gastrocnemius muscle and the Soleus muscle will be obtained in axial and Sagittal planes (both legs). The fat thickness and the skin thickness are being measured in both healthy and injured leg. Achilles tendon length will be measured using panoramic imaging sliding the probe from the calcaneus to the medial gastrocnemius. Cross-sectional area at the point of injury will be evaluated using regular ultrasound imaging. Elastic properties of the Achilles tendon will be measured using shear wave elastography. Shear wave elastography is a method available in some clinical ultrasound scanners that consists on generating shear waves in the tissue by sending high intensity ultrasound pulses. The speed of wave propagation is recorded by the scanner. The mechanical properties of the tissues are estimated from the values of the wave speed. For the area of lateral and medial gastrocnemius, the ultrasound probe is placed distally at a point 25% of tibial length from the medial tibial plateau. For the soleus, the ultrasound probe is placed proximally at a point 30% of tibial length from the medial malleolus. Extended field of view images are taken in short axis [55]. This ultrasound evaluation is not part of the standard of care for Achilles tendon rupture. The ultrasound evaluation will take place at the radiology suite at [name] (Hershey), the Biomechanics and imaging lab at [name] (State College), or Motion Analysis Lab (University of Delaware).

Self-reported diary and outcomes: To evaluate frequency of loading, from the day after surgery, participants will complete a diary (paper or electronic survey via REDCAP) on estimated daily weightbearing load, number of steps/days with a pedometer placed at the hip, and pain on a visual analogue scale (VAS). Although standard of care prescribes no weight-bearing during the first two weeks after repair, patients are active during that period of time. The level of activity (steps), even though does not involve the use of the injured limb, can help explain potential differences in self-reported outcomes, especially kinesiophobia scores. These measurements are not part of the standard of care. Self-reported outcomes will be also collected at weeks 6 and 12: the Achilles tendon Total Rupture Score (ATRS) [56], the Physical Activity Scale (PAS) [57], the Foot and Ankle Outcome Score (FAOS) Quality of Life subscale [58], and the Tampa Scale of Kinesiophobia (TSK) [59], [60]. Patient reported outcomes (ATRS, PAS and FAOS) are part of the standard of care for Achilles tendon rupture.

Single heel-rise tests: The ability of performing a single heel-rise will be evaluated at week 12. The participants will stand on a flat box with the ankle in neutral position and will be asked to perform a single heel-rise. The participants will be classified as being able to perform a one-legged heel-rise if they were able to lift the heel at least 2 cm once while keeping the knee straight [60]. MuscleLab® (Ergotest Technology, Oslo, Norway) measurement system will be used for the evaluations as previously described in our previous study [29]. This will be performed in the physical therapy clinic at [name]. This test is not part of the standard of care for Achilles tendon rupture.

Table 3. Study Procedures for Stimulation and control groups

Week	Procedure
1	Consenting, Randomization, Distribution of diary and activity monitor, Demonstration of NMES (stimulation group only), (in-person visit)
2, 4	Adjustment of NMES (stimulation group only), collection of steps, and diary data. (Visit 2 can be done virtually with a video call, visit four should be done in person.)
6	Ultrasound Imaging, Questionnaires (ATRS, PAS, FAOS, TSK), collection of steps and diary data, Discontinue use of NMES (stimulation group only). (In-person visit)
12	Ultrasound Imaging, Heel-rise test, Questionnaires (ATRS, PAS, FAOS, TSK) (In person visit)

7.2.1 Visit 1 (Week 1).

Provide a description of what procedures will be performed on visit 1 or day 1 or pre-test in order of how these will be done. If your study only involves one session or visit, use this section only and indicate 7.2.2 as not applicable.

This visit will be scheduled in first week after the surgery. The research team or clinician of the research team will demonstrate the NMES procedure to the participants. The research team will verify that the procedure is applied properly and follows with the protocol. An explanation of the information needed for the diary will also be provided. Participants will take the NMES device (for the treatment group) and the diary home and perform the procedure by themselves. Randomization will be communicated to the patient at this visit. Participants are provided the pedometer at this visit, and instructions on how to use it. The study team will not collect AEs at this visit. The total duration of this visit is estimated to be 45 minutes.

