9.4 Frequency of data collection

Describe the frequency of data collection, including when safety data collection starts.

Data about tendon healing will be collected at 6, and 12 weeks. Pain, weight bearing, and step count will be recorded daily for the first 6 weeks. Heel-rise evaluation will be performed at week 12.

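### The diary and pedometer cannot start the day after surgery if they are handed out at a first-week visit; start days will differ between participants, and no pain value precedes allocation or NMES.

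*Combined protocol and SAP*

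**What the plan says.** Three places set the expected coverage. In section 7.2, the paragraph on the self-reported diary says that "from the day after surgery, participants will complete a diary (paper or electronic survey via REDCAP"; it covers estimated weight-bearing load, pedometer steps and VAS pain. Section 7.1 states: "Other outcomes (activity level, pain) will be measured daily for the first 6 weeks after repair". Section 9.4 states: "Pain, weight bearing, and step count will be recorded daily for the first 6 weeks".

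Two places set when the materials arrive. The week 1 row of Table 3 lists "Consenting, Randomization, Distribution of diary and activity monitor, Demonstration of NMES (stimulation group only), (in-person visit". Section 7.2.1 says of visit 1 that "This visit will be scheduled in first week after the surgery", with no fixed day. For the pedometer it says: "Participants are provided the pedometer at this visit, and instructions on how to use it". For the diary: "An explanation of the information needed for the diary will also be provided". It adds: "Participants will take the NMES device (for the treatment group) and the diary home and perform the procedure by themselves". The participant is told the allocation at this same visit.

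Section 1.3 names steps and VAS pain as secondary endpoints. Section 8.3 plans summary statistics for reported pain. It gives no alignment by post-operative day and no rule for missing days. Section 7.4.5 marks blinding as not applicable.

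**The concern.** The stated start is met only when visit 1 falls on the first post-operative day. Otherwise the earliest days are missing, and the number missing depends on when the visit was booked. If pain falls during recovery, a participant who starts late will show a lower average over recorded days than one who starts early, with no true difference between them. Section 7.2 also wants activity during the two weeks without weight bearing to help explain kinesiophobia scores, and the missing days lie in that fortnight.

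Diary, pedometer, allocation and NMES device all arrive at one visit, and no section asks for a pain rating before disclosure or first stimulation. In an open-label trial with self-reported pain, every planned rating is then made by someone who knows their arm, and no pre-treatment value is available for adjustment.

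**Working it through.** **1. Days that can be recorded.** Inputs: six weeks = 42 days (sections 7.1 and 9.4); visit 1 on post-operative day d, with d from 1 to 7 (section 7.2.1). Recordable days are 42 − (d − 1) if recording starts on the day of the visit, or 42 − d if it starts the next day.

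| Visit 1 on day | Starts same day | Starts next day |
|---|---|---|
| 1 | 42 (0% lost) | 41 (2.4%) |
| 4 | 39 (7.1%) | 38 (9.5%) |
| 7 | 36 (14.3%) | 35 (16.7%) |

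At the extreme, 6 to 7 of the 14 non-weight-bearing days are lost (6/14 = 43%, 7/14 = 50%).

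**2. Could recording start earlier?** Section 7.2 allows an electronic diary and section 5.2.1 allows consent before surgery, so some pain and weight-bearing entries could in principle precede visit 1. No procedure describes this. It cannot supply steps, because section 7.2.1 gives out the pedometer only at visit 1. Any early entries would widen the spread of start days.

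**3. Effect on an unaligned pain average.** The documents give no pain trajectory, so the following are assumptions: a 0–10 scale; pain on day t equal to 1 + 5 × 0.5^((t − 1)/h), with half-life h of 5 to 14 days; or a straight-line fall from 6 to 2. The table gives the mean over recorded days to day 42, and the SD of that mean when start days are spread evenly over days 2 to 8 (next-day start after a visit on days 1 to 7).

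| Curve | Start day 1 | Start day 8 | Difference | SD, starts on days 2–8 |
|---|---|---|---|---|
| h = 5 | 1.92 | 1.41 | 0.50 | 0.13 |
| h = 7 | 2.24 | 1.73 | 0.51 | 0.14 |
| h = 10 | 2.68 | 2.20 | 0.48 | 0.13 |
| h = 14 | 3.16 | 2.72 | 0.43 | 0.12 |
| Linear | 4.00 | 3.66 | 0.34 | 0.10 |

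(Differences are taken before rounding.)

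The extreme pair differs by 0.34 to 0.51 points; the typical spread is 0.10 to 0.14. With an assumed between-person SD of 1.5 to 2 points, the added variance relative to the between-person variance runs from 0.10²/2² = 0.25% to 0.14²/1.5² = 0.9%; with an SD of 1 it is at most 0.14²/1² = 2%. With 25 per arm, the chance difference between arm means from this source has an SD of at most 0.14 × √(2/25) = 0.04 points.

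**4. Value of a baseline rating.** A covariate with correlation ρ removes a share ρ² of the outcome variance. For an assumed ρ of 0.4 to 0.6 this is 0.4² = 16% to 0.6² = 36%. The documents give no value for ρ.

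**The case against.** The strongest reply is that this is a wording slip with little consequence, and much of that stands. Start days have the same expected distribution in both randomised arms, the added noise is small, and 0.34 to 0.51 points describes two extreme participants, not the trial contrast. Section 8.3 does not define a 42-day mean, so the average used above is only an illustration of an unaligned summary. A randomised comparison is valid without a baseline value. A rating at visit 1 would itself fall on different post-operative days, so it needs that day alongside it in the model.

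A reader might go further and infer bias between arms, on the ground that training the stimulation group could shift its visit 1. The documents do not support this. Table 3 places consent and randomisation in the same week 1 visit for both arms, and section 7.2.1 has the allocation communicated there. Consent before surgery (section 5.2.1) and assignment of a code once the participant is consented (section 17.4) leave some room for earlier knowledge of the arm, but no section shows scheduling that depends on it.

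A reader might also wish to restrict the endpoints to days 8 to 42, which every participant can supply. That would discard the first week of stimulation in Table 2 and half of the non-weight-bearing fortnight, when alignment by post-operative day solves the problem without discarding data.

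What the reply does not remove is the contradiction itself, the absence of any alignment rule, and the absence of a pain value taken before the participant knows the arm.

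**Conclusion.** The point holds as an inconsistency with modest consequences. A day-after-surgery start cannot be met for steps unless visit 1 falls on that day. For pain, no procedure provides for it. Up to 14 to 17% of the diary period is unrecordable, and the actual spread of visit days is unknown. The resulting noise in unaligned pain averages is about 0.10 to 0.14 points, conditional on the assumed pain curves and evenly spread start days. The missing pre-treatment pain value costs precision only; the possible gain of 16 to 36% of variance depends on the assumed correlation. Bias between arms is not shown, and the week 12 heel-rise is untouched. The changes are worth making because they cost almost nothing and early days left unrecorded cannot be recovered.

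**What to change.** 1. Reconcile section 7.2 with Table 3 and section 7.2.1 by stating that the diary and pedometer start at visit 1, and amend sections 7.1 and 9.4 to match. Handing both out before surgery would also reconcile the text, but it needs consent and a contact before surgery for everyone.
2. Record each participant's start date. In section 8.3, compare pain and steps by post-operative day or week, using all recorded days, so that week 1 contributes whatever was collected.
3. Take one pain VAS at visit 1, before the allocation is disclosed and before any stimulation. Use it, with the post-operative day of visit 1, as a covariate in the pain comparison.

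The cost is one extra rating, a fixed order of steps at visit 1, and edits to the text. The downside is that week 1 data will be sparse. If visits were spread evenly over days 1 to 7 with a same-day start, about 25/7 ≈ 4 participants per arm would have a record for day 1 and 25 × 4/7 ≈ 14 for day 4. Week 1 estimates should be reported with the number contributing.
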